13.2 Sample Size/Accrual Rate

The primary goal of this Phase I trial is to determine the RP2D and assess safety of the combination regimen. A total of 6 -22 adolescent and young adult subjects will be accrued into the trial

It is anticipated that 0.5-1 subjects will be accrued per month so that study accrual will be completed within 36 months.

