5.2 Agent Administration

Treatment may be administered either in the inpatient or outpatient setting. Reported adverse events and potential risks are described in Section 7. Appropriate dose modifications are described in Section 6. No investigational or commercial agents or therapies other than those described below may be administered with the intent to treat the patient's malignancy.

Dose Escalation Schedule				
		Dose		
Dose Level	Irinotecan (mg/m ² /day)	Eribulin (mg/m²/dose)		
Level 0	90	0.8		
STARTING DOSE: Level 1	90	1.1		
Level 2	90	1.4		

There will be no intra-patient dose escalations.

Therapy Delivery Map – Cycle #		
	Patient name	DOB

DRUG	ROUTE	DOSAGE	DAYS	Observa	ations
Eribulin	IV over 2-5 min	See dose escalation scheme	1,8	a. 1 b. 1	History Physical Exam
Irinotecan	РО	90 mg/m ² /dose	1-5 (On day 1, irinotecan is given at least 15 minutes after eribulin)	c. (d. (e.)	(Ht/Wt/VS/ performance status) CMP CBC Pharmacokinetics ¹
Cefixime	PO	400 mg/day	-1 through 8		

Ht _____ Wt ____ BSA _____ Dose level = _____

Assigned Eribulin dose is $_{mg/m^2} = _{mg}$

Date	Date	Day	Eribulin	Irinotecan	Cefixime	Studies
Due	Given					
		-1 (20*)			mg	
		0 (21*)			mg	
		1	mg	mg	mg	a, b, c, d, e ¹
		2		mg	mg	
		3		mg	mg	
		4		mg	mg	$e (optional)^2$
		5		mg	mg	
		6			mg	
		7			mg	
		8	mg		mg	b, c^3 , d^4 , e^1
		15				c^{3}, d^{4}
		20			mg	
		21			mg	

¹Blood samples for pharmacokinetic testing will be obtained pre-dose, 0.25, 1, 1.5, 2, 4, and 5 hours after the administration of eribulin on day 1 and prior to day 8 dose with regularly obtained labs (see Appendix g for Pharmacokinetic Study Form). **These samples will only be collected in the first treatment cycle.**

² An optional single pharmacokinetic sample may be collected anytime between 24-96 hours if labs are being obtained at UK for other purposes.

³CMP must be drawn weekly during cycle 1, and then may be drawn only at the start of subsequent cycles ⁴CBC with differential should be drawn **twice weekly during the first cycle**, and then must be drawn at least weekly during subsequent cycles

On day 1 in which eribulin and oral irinotecan are administered concurrently, the eribulin should precede irinotecan by at least 15 minutes.

Subsequent cycles should start after day 21 as soon as the ANC \geq 1,000/µL and platelets \geq 100,000/µL, and eligibility criteria are met for renal and hepatic function (Section 3.1). This start date could vary by 3 days.

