5.6 Dose Escalating Criteria

A 3 + 3 design will be used to determine dose assignment for patients, as described in Section 13.2. Specifically, the following rules will apply for dose escalation:

- A. Evaluate 3 patients at $dose_k$:
 - 1. If 0 of 3 patients have DLT, then
 - i. If first cohort, increase dose to $dose_{k+1}$ and go to A.
 - ii. Otherwise, go to B.
 - 2. If 1 of 3 patients has DLT, then go to B.
 - 3. If more than 1 patient has DLT
 - i. If lowest dose, then go to C.
 - ii. Otherwise, decrease dose to $dose_{k-1}$ and go to A.
- B. Evaluate 3 additional patients at dose_k :
 - 1. If 0 or 1 of 6 patients has DLT, then increase dose to $dose_{k+1}$ and go to A.
 - 2. If 2 or more patients have DLT, then
 - i. If lowest dose, then go to C.
 - ii. Otherwise, decrease dose to $dose_{k-1}$ and go to A.
- C. Discontinue dose escalation/de-escalation.

Accrual will continue until the recommended phase II dose for a Phase II study (RP2D) is established and at least 6 patients have been treated at this dose. The RP2D is the highest dose level at which no more than 1 of 6 patients experiences first-cycle DLT. Doses higher than dose level 2 will not be studied in this trial. Once the RP2D is identified, an additional 10 patients will be enrolled at this dose level.

5.7 **Duration of Therapy**

In the absence of treatment delays due to adverse event(s), treatment may continue for up to 17 cycles until one of the following criteria applies:

• Disease progression

- Intercurrent illness that prevents further administration of treatment
- Unacceptable adverse event(s)
- Patient decides to withdraw from the study
- General or specific changes in the patient's condition render the patient unacceptable for further treatment in the judgment of the investigator.

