13. STATISTICAL CONSIDERATIONS

13.1 Study Design/Endpoints

A phase I, dose-escalation trial is proposed to determine the recommended phase II dose (RP2D) of escalating doses of eribulin in combination with standard-dose oral irinotecan. Cohorts of 3 patients per dose level are proposed using a 3+3 design [70, 71]. The following rules will be incorporated for dose escalation/de-escalation and establishing the recommended Phase II dose using the occurrence of DLT during the first cycle of therapy that is possibly, probably, or definitely attributable to study therapy.

A. Evaluate 3 patients at dose_k:

- 1. If 0 of 3 patients have DLT, then
 - i. If first cohort, increase dose to $dose_{k+1}$ and go to A.
 - ii. Otherwise, go to B.
- 2. If 1 of 3 patients has DLT, then go to B.
- 3. If more than 1 patient has DLT

- i. If lowest dose, then go to C.
- ii. Otherwise, decrease dose to $dose_{k-1}$ and go to A.
- B. Evaluate 3 additional patients at dose_k:
 - 1. If 0 or 1 of 6 patients has DLT, then increase dose to $dose_{k+1}$ and go to A.
 - 2. If 2 or more patients have DLT, then
 - i. If lowest dose, then go to C.
 - ii. Otherwise, decrease dose to $dose_{k-1}$ and go to A.
- C. Discontinue dose escalation/de-escalation.

The RP2D is defined as the highest dose level in which there is no more than 1 DLT in 6 patients. Ten additional patients will be enrolled at the RP2D level. Similar dose modifications as specified in Section 6 would be applied to these patients. Doses higher than dose level 2 will not be studied in this trial.

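### Section 13.2: the ceiling of 22 patients is below the 28 that the 3+3 rules permit, and 36 months is too short at the lower stated accrual rate

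*Combined protocol and SAP*

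**What the plan says.** Section 13.2 gives the size, "A total of 6 -22 adolescent and young adult subjects will be accrued into the trial", and the timing: "It is anticipated that 0.5-1 subjects will be accrued per month so that study accrual will be completed within 36 months". It shows no derivation for either.

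The design that generates these numbers is set out elsewhere:

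- The dose table in Section 5.2 has Levels 0, 1 and 2, and marks "STARTING DOSE: Level 1".
- Section 13.1 states "Cohorts of 3 patients per dose level are proposed using a 3+3 design" and "Doses higher than dose level 2 will not be studied in this trial".
- The algorithm in 5.6 and 13.1 escalates the first cohort after 0 of 3 with DLT. It sends any level above the lowest with 2 or more DLTs down one level and back to step A.
- Section 13.1: "The RP2D is defined as the highest dose level in which there is no more than 1 DLT in 6 patients".
- Section 5.6 continues accrual until the RP2D "is established and at least 6 patients have been treated at this dose", and then: "Once the RP2D is identified, an additional 10 patients will be enrolled at this dose level".

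**The concern.** A stated range of 6 to 22 should be the smallest and largest totals the rules can produce. The lower end is exactly that: the shortest possible trial. The upper end appears to count only two of the three dose levels. The paths left out are those where Levels 2 and 1 both prove too toxic after an initial 0 of 3 at Level 1. On such a path the trial would reach its stated total after de-escalating for toxicity, before the expansion at Level 0 is full. Section 5.6 would require accrual to continue, and the total in 13.2 would have to be amended during the trial, with IRB approval before implementation (Section 12.3).

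The accrual sentence presents 36 months as following from the whole range of 0.5 to 1 per month. If it fails at the lower end, the planned duration rests on an unstated assumption about which part of the range will be achieved.

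**Working it through.** **Inputs.** Cohorts of 3 (13.1); Levels 0, 1 and 2, starting at Level 1 (5.2); escalation and de-escalation rules (5.6, 13.1); 6 patients required at the RP2D with no more than 1 DLT (5.6, 13.1); 10 additional patients once the RP2D is found (5.6, 13.1); 0.5 to 1 patients per month and 36 months (13.2).

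**Reading of the rules.** The first cohort is the trial's first cohort. Counts accumulate to at most 6 per level. Escalation stops at success at Level 2, or at success just below a level that has already failed. The expansion is filled only if an RP2D is found.

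**The plan's own figures.**

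- Lower limit: 2 or more DLTs in 3 at Level 1, then 2 or more in 3 at Level 0, then stop. 3 + 3 = 6. This reproduces.
- Upper limit: 22 is obtained as 2 × 6 + 10, that is, two full levels and the expansion.

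**Largest total under the rules.**

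| Step | Outcome | Patients |
|---|---|---|
| Level 1 | 0 of 3, escalate | 3 |
| Level 2 | 0 or 1 of 3, then 2 or more of 6, de-escalate | 6 |
| Level 1 | 3 more, 2 or more of 6, de-escalate | 3 |
| Level 0 | no more than 1 of 6, RP2D | 6 |
| Expansion | | 10 |
| Total | | 28 |

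If Level 2 fails after its first 3 patients, the total is 28 − 3 = 25. Enumerating every path gives totals of 6, 9, 12, 15 and 18 when no RP2D is found, and 19, 22, 25 and 28 when one is.

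**Smallest total with an RP2D.** Each possible RP2D needs at least 9 escalation patients: 3 at Level 1 + 6 at Level 2; 6 at Level 1 + 3 at Level 2; or 3 at Level 1 + 6 at Level 0. So 9 + 10 = 19.

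**How likely.** The documents state no DLT rates. Exact path probabilities under four assumed sets:

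| Assumed DLT rate, Levels 0/1/2 | P(total > 22) | P(total > 18) |
|---|---|---|
| 5/10/20% | 0.7% | 99.7% |
| 25/40/50% | 3.6% | 65% |
| 5/20/40% | 4.0% | 98.9% |
| 5/40/60% | 7.1% | 97.5% |

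**Duration.** In 36 months, 0.5 × 36 = 18 patients and 1 × 36 = 36 patients. Months needed = N ÷ rate; rate needed = N ÷ 36.

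| N | Months at 0.5 | Months at 1 | Rate needed for 36 months |
|---|---|---|---|
| 19 | 38 | 19 | 0.53 |
| 22 | 44 | 22 | 0.61 |
| 28 | 56 | 28 | 0.78 |

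**Sensitivity to the reading.** If returning to step A means a fresh cohort, the longest path is 3 (Level 1) + 6 (Level 2) + 6 (Level 1 again) + 6 (Level 0) + 10 = 31. This stops the search as soon as Level 1 already has no more than 1 DLT in 6 and Level 2 has failed, because Level 1 then meets the RP2D definition.

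**The case against.** There are three serious counter-arguments.

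First, 28 is not literally derivable either. Step B.1 always says to increase the dose, and the discontinuation step is reached only from the lowest dose. Read word for word, the algorithm never stops after success and has no finite maximum. With fresh cohorts and no stop, one could also reach 6 + 6 + 6 + 6 + 10 = 34. Much of this is answered by the text: the RP2D definition, the Level 2 cap and the rule that accrual continues until the RP2D is established together supply the stopping points. The 34-patient path carries on after Level 1 already meets the definition. What stands is that cumulative counting is an assumption. Nor do these totals allow for replacing patients not evaluable for DLT, and any replacement would add to them.

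Second, totals above 22 are rare, no test or precision statement depends on 22, and 12.3 provides an amendment route. That is true and limits the severity. It does not make 22 the upper limit, particularly as the lower limit of 6 is itself an extreme path (0.02% to 5.5% in the four scenarios).

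Third, the 36 months is a forecast over a range. It holds for 22 patients at 0.61 per month or more, and at the midpoint of 0.75 they take 22 ÷ 0.75 = 29.3 months. The 19-against-18 gap is one patient, or two months. All of this is correct. The P(total > 18) figures matter only if accrual stays near 0.5 per month, and the documents give no probability for that. The sentence nevertheless offers 0.5 per month as compatible with 36 months, and it is not.

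**Conclusion.** The concern holds. Under cumulative counting the rules give 6 to 28 patients, not 6 to 22; under fresh cohorts the maximum consistent with the RP2D definition is 31, further still from 22. The practical chance of passing 22 is small, 0.7% to 7.1% in the assumed scenarios.

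The duration error needs no assumed DLT rate. At the plan's own lower accrual rate, no trial that finds an RP2D and fills the expansion finishes in 36 months, and the plan's own 22 patients overrun by 8 months (44 − 36). Towards the upper part of the accrual range the statement is sound.

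Neither error affects the validity of the dose-finding rules or any analysis. Both figures should be corrected, but this does not threaten the trial's conclusions.

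**What to change.** In Section 13.2:

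1. Restate the total as 6 to 28 patients: up to 18 in escalation over three dose levels, plus 10 in expansion. Say that 28 rests on counting all patients treated at a level together. If fresh cohorts on return to a level are intended, the figure is 31. The sponsor should state which applies.
2. Restate accrual at 0.5 to 1 per month as 22 to 44 months for 22 patients and 28 to 56 months for 28. Alternatively, keep 36 months and state the rate it requires: 0.61 per month for 22 patients, 0.78 for 28.

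The cost is two restated figures and a sentence on counting. The escalation rules, doses and analyses are unchanged. The only downside is that the stated size and duration look less favourable.

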13.3 Stratification Factors

Not applicable for this trial

13.4 Analysis of Primary and Secondary Endpoints

All patients who received study drug will be included in the safety analysis of this combination regimen. Dose-limiting toxicity rate, adverse event data and corresponding toxicity grades during the days of treatment will be summarized in each dose level and in the overall patient population. Incidence tables will be generated to summarize incidence of patients reporting at least one episode of each specific adverse event, incidence of adverse events causing withdrawal and incidence of serious adverse events. The total number of episodes for each event reported (Frequency Table), and the severity and attribution to study therapy of each episode reported (Severity Table and Attribution Table) will also be displayed.

Listings of adverse events by patients will include the time to onset, the duration of each event, the severity of each event, and the relationship of the event to study therapy, whether it was a serious event, and whether it caused withdrawal. Safety data will be summarized for the overall patient group and by dose levels. Toxicities will be graded according to Common Toxicity Criteria (CTCAE) v4.02.

Estimates of antitumor effect based on RECIST 1.1 criteria will be estimated. Furthermore,

Protocol # 15-0659 Version Date: March 22, 2017

specific PD parameters will be assessed including SN-38 and SN-38 glucuronide. Descriptive statistics will be employed to summarize quantitative levels of PD parameters at each time point of follow-up while changes in PD from baseline will be calculated and compared using paired statistical tests. Pharmacokinetic modeling (two-compartment or non-compartmental models) will be employed to estimate several PK parameters (area under the concentration versus time curve, AUC, half-life, clearance, Cmax, etc). These analyses will be considered exploratory in this Phase I trial.

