5.5 Definition of Dose-Limiting Toxicity

Dose-limiting toxicity (DLT) will be defined as any of the following events, detailed in Sections 5.5.2 and 5.5.3 that are possibly, probably or definitely attributable to protocol therapy. Decisions regarding the estimation of the recommended phase II dose and assigning treatment dosages to subsequent patients will be made on observations occurring in the first cycle of therapy.

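### The DLT rate planned for the RP2D combines six escalation patients selected for at most one DLT with ten unselected expansion patients, so the reported rate is biased low

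*Combined protocol and SAP*

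**What the plan says.** Section 13.1 gives the selection rule: "The RP2D is defined as the highest dose level in which there is no more than 1 DLT in 6 patients". Section 5.6 has the same rule and requires that "at least 6 patients have been treated at this dose". Section 13.1 continues: "Ten additional patients will be enrolled at the RP2D level". Section 5.5 states that dose decisions "will be made on observations occurring in the first cycle of therapy".

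For the analysis, section 13.4 states: "All patients who received study drug will be included in the safety analysis of this combination regimen". It then says that the DLT rate, with adverse events and grades, "will be summarized in each dose level and in the overall patient population", and later repeats that safety data are shown overall and by dose level. It does not ask for the expansion cohort on its own. It plans no interval and no adjusted estimate for the DLT rate.

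**The concern.** Escalation and expansion patients at the RP2D share one dose level, so a summary by dose level puts them in one row. Section 13.4 does not use the word pooling, but this is its direct reading.

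The two groups do not carry the same information. The six escalation patients are there because they had 0 or 1 DLT; had they had two or more, the level would not be the RP2D. Their observed rate cannot exceed 1/6 (17%), whatever the true rate is. The ten expansion patients enter after the dose is fixed and are not selected on outcome. Combining the groups pulls the reported rate below the truth on average.

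At stake is how a reader takes the safety estimate at the dose that goes forward. The understatement grows as the true rate rises, so it is largest where a too-toxic level has passed by chance. The plan does not display the one group at that dose that is free of the selection.

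**Working it through.** **The plan's own figure.** The only design figure is in section 13.2: "A total of 6 -22 adolescent and young adult subjects will be accrued into the trial". The lower end is 3 + 3 = 6 (levels 1 and 0 each fail in three patients, so no RP2D and no expansion). The upper end is 6 + 6 + 10 = 22 (two full levels plus the expansion). Both reproduce, and the second implies 6 + 10 = 16 patients at the RP2D. No DLT rate, precision or operating characteristic is stated.

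**Inputs.**
- At most 1 DLT in 6 at the RP2D (sections 5.6 and 13.1).
- Ten expansion patients at that level (section 13.1).
- True first-cycle DLT probability *p* at that level: not in the documents. Assumed range 5% to 40%.

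**Formulas.** Let X be the DLT count in the six, Binomial(6, *p*), observed only when X ≤ 1.
- Probability that the level passes: (1-p)^6 + 6p(1-p)^5.
- Expected rate in the selected six: 6p(1-p)^5 / [(1-p)^6 + 6p(1-p)^5] / 6, which simplifies to p/(1+5p).
- Expected combined rate: [6 × p/(1+5p) + 10p]/16.
- Bias: combined rate minus *p*.

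**Example at p = 20%.** Selected six: 0.20/2.0 = 0.100. Combined: (6 × 0.100 + 10 × 0.20)/16 = 2.6/16 = 0.1625. Bias: -3.75 points.

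| True rate (assumed) | Level passes | Selected six | Combined 16 | Bias (points) | RMSE, combined | RMSE, ten alone |
|---|---|---|---|---|---|---|
| 5% | 97% | 4.0% | 4.6% | -0.4 | 0.051 | 0.069 |
| 10% | 89% | 6.7% | 8.75% | -1.25 | 0.068 | 0.095 |
| 20% | 66% | 10.0% | 16.25% | -3.75 | 0.093 | 0.126 |
| 25% | 53% | 11.1% | 19.8% | -5.2 | 0.104 | 0.137 |
| 33% | 36% | 12.5% | 25.3% | -7.7 | 0.124 | 0.149 |
| 40% | 23% | 13.3% | 30.0% | -10.0 | 0.141 | 0.155 |

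The ten alone have expected rate *p* and RMSE √(p(1-p)/10).

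**Check on the full path.** Whether the next level up fails depends on other patients, so it does not offset the truncation. Exact enumeration of the printed 3 + 3 rules, completing a level to six when the trial returns to it, gives the same expected rates at each selected level. Averaged over whichever level is selected, the bias is -2.65 points for assumed rates of 5%, 10% and 20% at levels 0, 1 and 2; -3.94 for 10%, 20% and 30%; and -5.86 for 20%, 30% and 45%.

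**The case against.** **No decision uses the combined rate.** The RP2D is fixed on the first six patients, before the expansion starts. Section 13.4 plans a descriptive summary, and as a description of what was observed the combined row is accurate. This stands. A reader might infer that the choice of dose is compromised; it is not.

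**The importance can be overstated.** A reader might take this rate to be the main figure handed to the phase II design. The documents do not say so. The primary objective (1.1.1) is a dose, toxicity and DLTs are a secondary objective (1.2.1), and section 2.1 says only that the study will inform the design of a phase II trial.

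**The large biases are the less likely ones.** A level at 40% passes only 23% of the time, while at 5% and 10% the bias is -0.4 and -1.25 points. At 20% the bias of 3.75 points is well below the sampling standard deviation for 16 patients, √(0.2 × 0.8/16) = 10 points. This stands, and is why the whole range is shown.

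**Intervals are hardly affected.** A reader might infer that intervals around the combined rate would often miss the truth. The plan contains no such interval. If an exact 95% interval were added, it would lie wholly below the truth 7.1% of the time at 40% (1.8% without selection), 4.1% at 33%, and no more than 1.9% at the rates checked up to 30%.

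**The combined rate is the more accurate single number.** Its RMSE is lower at every rate in the table. This stands, and rules out replacing it with the expansion rate.

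**The split is nearly recoverable.** Section 13.4 plans listings by patient, and a reader who knows the rule knows that the first six contributed 0 or 1 DLT. That is true, but it leaves the reader to do what one table could show.

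**The all-patient DLT rate.** It averages up to three eribulin levels with weights set by the escalation path, so one might want it removed. Nothing in section 13.4 claims that it estimates the rate at any dose, and as a safety total it does no harm if labelled.

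**Conclusion.** The point holds as a low-severity reporting improvement. Followed as written, section 13.4 gives a DLT rate at the RP2D that is biased low. The direction is certain for any true rate strictly between 0 and 1. The size rests on an assumed rate: under 1.5 points up to a true 10%, about 4 to 5 points at 20% to 25%, and 8 to 10 points at 33% to 40%, where a level is less likely to be selected.

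This assumes six escalation patients at the RP2D, an expansion that runs to its fixed ten (section 13.1 states no DLT-based stopping rule for it), and independent patients with a common rate. If a return to a lower level means fresh cohorts instead of completion to six, the number at the RP2D could exceed 16 and the figures would shift. The documents do not support reading this as a flaw in how the RP2D is chosen, or as grounds to discard the six escalation patients.

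**What to change.** In section 13.4, report the first-cycle DLT rate at the RP2D in three rows: escalation patients, expansion patients, and both combined, each with an exact 95% interval. Add a footnote that the escalation and combined rows are conditioned on at most 1 DLT in 6, and that the expansion row is free of that selection but less precise. Keep the all-patient DLT summary if wanted, labelled as a descriptive total that does not estimate the rate at any one dose.

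The cost is a few lines of analysis text and two table rows; no patients, data or procedures are added. The downside is the width of the expansion-only interval: 2 DLTs in 10 would give 2.5% to 55.6%. That is why the combined row should stay beside it.
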